7.0 STUDY AGENT ADMINISTRATION

Patients will be treated with Eribulin 1.4 mg/m² administered on days 1 and 8, repeated every 21 days.

AGENT	DOSE	ROUTE	DAYS	ReRx INTERVAL
Eribulin	1.4 mg/m ²	i.v. bolus over 2-5 mins	1,8	3 weeks

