8.2 RECOMMENDED DOSE DELAYS

As a general rule, participants should be assessed for peripheral neuropathy and complete blood count lab values should be obtained and reviewed prior to each dose.

- Do not administer eribulin on Day 1 or Day 8 if any of the following parameters are evident:
 - ANC < 1,000/mm³
 - Platelets < 75,000/mm³
 - Grade 3 or 4 non-hematological toxicities (Section 8.2 and 8.3 have additional details)
- The Day 8 dose may be delayed for a maximum of 1 week:
 - If toxicities do not resolve or improve to ≤ Grade 2 severity by Day 15, omit the dose
 - If toxicities resolve or improve to a ≤ Grade 2 severity by Day 15, administer eribulin at a reduced dose and initiate the next cycle no sooner than 2 weeks later

The following chart is a representation of dose modifications per event. Consult the principal investigator for additional information.

EVENT DESCRIPTION	RECOMMENDED ERIBULIN DOSE
Permanently reduce the 1.4 mg/m ² eribulin dose for any of the following:	

○ ANC <500 cells/mm³ for >7 days○ ANC <1,000 cells/mm³ with fever or infection○ Platelets <25,000/mm³○ Platelets <50,000/mm³ requiring transfusion○ Non-hematologic Grade 3 or 4 toxicities○ Omission or delay of Day 8 dose in previous cycle for toxicity	1.1 mg/m ²

EVENT DESCRIPTION	RECOMMENDED Eribulin DOSE
Occurrence of any event requiring permanent dose reduction while receiving 1.1 mg/m2	0.7 mg/m2
Occurrence of any event requiring permanent dose reduction while receiving 0.7 mg/m2	Discontinue eribulin

Note: if subject meets criteria to be removed from study due to toxicity but is deemed to have clinical benefit from treatment, continuation of treatment and reduction or modification of the dose can be discussed with the principal investigator.

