8.3 TREATMENT REMOVAL

Patients will be removed from treatment in the event of:

- Peripheral neuropathy Grade >2 that does not improve as in Section 8.1
- Grade 3 or 4 hypersensitivity/infusion reaction.
- Inability of subject to comply with study requirements.
- Determination by the investigator that it is no longer safe for the subject to continue therapy.
- Progression of disease (as defined in Section 10.1).
- Delay of treatment \geq 2 weeks.
- Patient may choose to withdraw her participation at any time for any reason

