8.5 SERIOUS ADVERSE EVENT REPORTING

Where **adverse drug reaction** is defined as:

A noxious and unintended response to a medicinal product related to any dose. A causal relationship between the medicinal product and the adverse response is at least a reasonable possibility.

And **serious** is defined as:

A serious adverse event (experience) or reaction is any untoward medical occurrence that at any dose:

- Results in death
- Is life threatening

(Note: the term life-threatening in the definition of “serious” refers to an event in which the subject was at risk of death at the time of the event; it does not refer to an event which hypothetically might have caused death if it were more severe)

- Requires inpatient hospitalization or prolongation of existing hospitalization
- Results in persistent or significant disability/incapacity, or
- Is a congenital anomaly/birth defect

Medical and scientific judgment should be exercised in deciding whether expedited reporting is appropriate in other situations, such as important medical events that may not be immediately life-threatening or result in death or hospitalization but may jeopardize the subject or may require interventions to prevent one of the other outcomes listed in the definition above. These should also usually be considered serious.

All Serious Adverse Events (SAEs) will be reported to the IRB. Also, the Principal Investigator will report SAEs via the MedWatch Form 3500A to the FDA, which can be accessed at:

<http://www.accessdata.fda.gov/scripts/MedWatch/>

MedWatch forms will be sent to the FDA online at the above internet address or to the following:

MEDWATCH

[name]

[name]

FAX: [name] ([name])

The notification of a serious suspected adverse drug reaction should occur as soon as possible, but no later than one business day, and should be done by fax or email via the Eisai standard serious adverse event report form (attached hereto as Appendix B). The contact details for the notification are:

Eisai Medical Services
[name]
[name]
[contact]
[contact]
Email: [contact]

In addition, the Principal Investigator agrees to notify Eisai immediately of any other information that suggests a change to the safety profile of the Study Drug.

9.0

CLINICAL AND LABORATORY EVALUATIONS AND STUDY CALENDAR

Parameter	Pre-Treatment ⁵	Each Cycle ¹	Every 2 Cycles	Every 4 Cycles	Follow-Up (every 3 mos.) x 2 yrs	End of Study

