History & Physical Exam	X	X			X	
Weight, Performance Status	X	X				
Toxicity Assessment		X Day 1 and 8				
WBC (differential), Hgb, platelets	X	X Day 1 and 8				
Electrolytes, MG, BUN, Cr	X	X				
LFT (Bilirubin, AST, ALT, Alkaline phosphatase		X				
EKG	X			X		
CXR	X		X ⁶			
Radiology, x-ray or Scans for disease measurement	X		X			
Tissue collection ³	X					
Peripheral Blood Collection for Correlative Studies		X ⁴				X
Eribulin		Day 1 and 8				

¹ Within 24 hrs² As clinically indicated³ From paraffin embedded prior biopsy⁴ Cycles 1-6⁵ Within 28 days of each cycle⁶ CXR is only required in the event that a CT of the chest is not done. Should a CXR be given in place of a CT scan, an additional CXR should be repeated every 2 cycles.

10.0**CRITERIA FOR EVALUATION AND ENDPOINT DEFINITIONS**

The outcome status (in terms of toxicity, response, reason off study, progression, and survival) of all eligible patients will be reported. All eligible patients who begin treatment will be included in the analysis of response, survival and time-to-failure.

Toxicities and adverse events including laboratory adverse events will be graded and summarized according to the National Cancer Institute CTCAE, v4.3 (available on the NCI website at: <http://ctep.cancer.gov/forms/CTCAEv4.pdf>).

Response will be evaluated according to the RECIST criteria v1.1:

Eligibility

Only patients with measurable disease (at least one measurable lesion) at baseline should be included in protocols where objective tumor response is the primary endpoint.

Measurable lesions - lesions that can be accurately measured in at least one dimension with longest diameter ≥ 10 mm and 2x slice thickness on CT scan. Lymph nodes must be ≥ 15 mm in **short axis**. Bone lesions may be measurable if there is a lytic/soft tissue component that meets minimum size criteria. CXR lesions must be > 20 mm.

Non-measurable lesions - all other lesions, including small lesions or lesions not conventionally measurable (i.e. leptomeningeal disease, ascites, pleural/pericardial effusion, inflammatory breast disease, lymphangitis cutis/pulmonis, cystic lesions, and also abdominal masses that are not confirmed) should be noted and followed by imaging techniques but not measured.

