10.1.3 PRIMARY TOXICITY ENDPOINTS

The primary toxicity endpoint is any occurrence of grade 3+ hematologic and non-hematologic toxicity according to CTCAE4.3.

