12.4. DATA COLLECTION FORMS AND SUBMISSION SCHEDULE

All data will be collected using USC CISO data collection forms. The original data collection forms will reside at USC in secure location.

- Within two weeks of registration, the data manager will complete the On-Study Form (Form OS).
- Within two weeks of completion of each course of treatment, the data manager must complete the following:

Treatment and Adverse Event Form

Supplemental Data Form (if applicable)

Flow Sheets (These are to be submitted along with each treatment form.)

Each time a patient is evaluated for response and/or new follow-up information is obtained the data manager will complete the Response/Off-Study/Follow-Up Form.

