Interim Monitoring of Toxic Death. The occurrence of toxic death (TD) at any time will be a primary endpoint for safety monitoring. A population TD rate that exceeds $p=0.05$ will be considered unacceptable. Monitoring will be based on a Bayesian rule on the binomial frequency of TD using a Beta(1,3) prior. A posterior probability of $\geq 90\%$ that the population TD rate p exceeds 0.05 will be sufficient to require that the cause and circumstances of the TDs be reviewed immediately with the study committee and with the Data and Safety Monitoring Committee to determine whether modifications to or termination of the study are warranted. Operationally this will occur if 1 TD occurs within the first 8 patients, or 2 occur

within the first 19 patients. A posterior probability of $\geq 97.5\%$ that p exceeds 0.05, with the occurrence of at least 2 TDs, will be considered very compelling evidence that the population toxic death rate exceeds 5%, and will require immediate termination of the study unless a convincing rationale for continuing the study exists. Operationally this will occur when 2 TDs within the first 10 patients, 3 within the first 19, or 4 during the study are observed.

Analysis of correlative endpoints. The analysis of GRP78 IHC score and GRP78 serum level, as well as other correlative markers (e.g. Tau-protein, alpha- & beta-tubulin), will be analyzed via Cox regression analysis for PFS, and via logistic regression for BOR rate. The power of these analyses is difficult to determine, since there is little preliminary data on the distribution of these endpoints in tumor and serum. However, the power of these analyses can be appreciated from the following. If, for example, GRP78 IHC level is divided at the median, and BOR rate is 25% with Eribulin in this population, there will be 73% power to detect a difference in BOR rate of 5% vs 45% in the two resulting group, based on a two-sample two-sided test of proportions with 5% Type I error. Hence it is likely that only profound associations between measures of efficacy and levels of GRP78 and other correlative endpoints will be detectable. Actually analyses based on ordered categorical and continuous measures will be somewhat more powerful than this. Similar considerations apply to the other correlative endpoints that will be studied.

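### No toxicity check or safety blood test is scheduled after a patient's final dose, so non-fatal grade 3+ events can be under-recorded, and no rule says which deaths count as toxic

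*Combined protocol and SAP*

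**What the plan says.** - **Calendar (Section 9.0).** The row "Toxicity Assessment" and the on-treatment blood counts carry marks for Days 1 and 8 of each cycle. Chemistry and liver tests are marked once per cycle. All these rows are blank under "Follow-Up (every 3 mos.) x 2 yrs" and under End of Study. The follow-up column holds history and physical examination; the End of Study column holds the correlative blood draw, which Section 11.0 places at the end of study drug.
- **Timing of checks (Section 8.2).** The protocol recommends that "participants should be assessed for peripheral neuropathy and complete blood count lab values should be obtained and reviewed prior to each dose".
- **Dosing (Section 7.0).** Eribulin is "administered on days 1 and 8, repeated every 21 days".
- **Toxicity endpoints.** Section 10.1.3 takes "any occurrence of grade 3+ hematologic and non-hematologic toxicity" as the primary toxicity endpoint. Section 13.0 computes grade 3+ rates for course 1 and for all courses combined.
- **Toxic death (Section 13.0).** "The occurrence of toxic death (TD) at any time will be a primary endpoint for safety monitoring". No rule is given for deciding that a death is toxic.
- **Forms (Section 12.4).** A treatment and adverse event form is due within two weeks of completing each course. At response evaluations and when new follow-up information arrives, "the data manager will complete the Response/Off-Study/Follow-Up Form".
- **Reporting (Sections 8.4 and 8.5).** SAEs go to the IRB, and serious suspected reactions in anyone exposed go to the drug supplier. Neither duty has an end date.

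**The concern.** The endpoint covers any grade 3+ event, but the schedule that finds such events works only while another dose is due. After a Day 8 dose the next scheduled check is Day 1 of the following cycle, 14 days later. A patient who stops has no following cycle, and her next calendar contact with any clinical examination is a 3-monthly visit with no toxicity or blood-count mark.

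What is at stake is the grade 3+ rate, the trial's main safety result. Section 4.0 lists grade 3+ neutropenia at 57% and grade 3+ peripheral neuropathy at 8%. Neutropenia is a laboratory finding and may never be seen if no blood is taken. The all-courses rate can therefore be too low. The course 1 rate is affected only for patients who stop during or after course 1.

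A second, smaller matter is the toxic-death rule. It acts on very few events and depends on each death being classified as related or not, yet the plan does not say how.

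**Working it through.** **1. Does any scheduled check follow the last dose?**

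| Source after the last dose | What it provides | Scheduled toxicity check or blood count? |
|---|---|---|
| Section 9.0, each-cycle column | Days 1 and 8, before dosing (Section 8.2) | Not once no further dose is due |
| Section 9.0, End of Study | Correlative blood | No |
| Section 9.0, follow-up | History and physical, 3-monthly for 2 years | No |
| Section 12.4, course form | Entry deadline for the data manager | No |
| Sections 8.4 and 8.5 | Reporting of events already known | No |

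**2. How many intervals are involved? (illustration)**

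Assumptions, not in the plan: exponential PFS, and stopping only at progression on the scans done every 2 cycles (6 weeks). Inputs from Section 13.0: 6-month PFS of 10% and 26%. Six months is taken as 26 weeks.

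- Weekly hazard h = −ln(PFS6)/26: 0.0886 and 0.0518.
- Chance of stopping at each scan = 1 − exp(−6h): 0.412 and 0.267.
- Mean cycles = 2/(1 − exp(−6h)): 4.85 and 7.49.
- Each cycle has one post-Day-8 interval and each patient one final interval, so the unchecked share is 1/(mean cycles): 0.206 and 0.134.

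These are shares of intervals. The endpoint is per patient, and a patient is misclassified only if her sole grade 3+ event falls after the last dose and is not found otherwise. The documents give no probability for that. In this model nobody stops after one course, so it says nothing about the course 1 rate.

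**3. The toxic-death boundaries.**

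With the Beta(1,3) prior, x deaths in n patients give a Beta(1+x, 3+n−x) posterior. The probability that the rate exceeds 0.05 is:

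| Deaths/patients | Posterior probability | Plan's threshold |
|---|---|---|
| 1/8 | 0.898 | 0.90 (review) |
| 2/19 | 0.905 | 0.90 (review) |
| 2/10 | 0.9755 | 0.975 (termination) |
| 3/19 | 0.9778 | 0.975 (termination) |
| 4/30 | 0.9770 | 0.975 (termination) |

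Four boundaries reproduce exactly and 1 in 8 falls just short. None depends on the visit schedule, but all assume that every toxic death is counted as one.

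**4. What non-attribution would do (illustration).**

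Suppose a fraction m of toxic deaths is not classified as toxic; the documents give no value for m. The counted rate is then p(1 − m). Exact recursion of the stated boundaries over 30 patients gives:

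| True rate p | m | Reaches review | Reaches termination |
|---|---|---|---|
| 10% | 0 | 70% | 46% |
| 10% | 25% | 57% | 29% |
| 10% | 50% | 40% | 13% |
| 15% | 0 | 87% | 75% |
| 15% | 25% | 75% | 54% |
| 15% | 50% | 57% | 29% |

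**The case against.** The strongest reply is that patients do not vanish after the last dose. They have a history and physical every 3 months for 2 years, and an adverse event form is due for every course, including the last, whose 21 days contain the interval after its Day 8 dose. This stands as far as it goes, and a reader should not infer that nothing is assessed after the last dose. But a form deadline does not create an examination or a blood count, and a 3-monthly physical will not find a transient neutropenia.

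A reader might also infer that a late toxic death would be missed. The documents do not support that. Death is a serious event under Section 8.5, reporting has no end date, all-cause death is followed for overall survival (Section 10.1.2), the count runs without time limit, and the DSMC reviews severe events in real time (Section 15.2). The Section 8.5 definition of an adverse drug reaction also asks for a causal judgement. What remains is that nothing links that judgement to the Section 13.0 count or requires it for every death.

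A third tempting reading is that patients removed for toxicity are the ones whose toxicity is lost. Mostly the reverse holds. Removal for "Peripheral neuropathy Grade >2 that does not improve as in Section 8.1" presupposes that the event was seen, and a patient who attends for a dose that is then withheld has been checked. Her event is already counted. The gap concerns mainly patients who stop for another reason, such as progression, without a further dosing visit.

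Finally, the calendar was read from a flattened table, the footnote on clinical indication has lost its anchor, and the data forms and the institutional monitoring plan are not in the documents. An as-indicated test would still not be a scheduled one, but local practice may already close part of the gap.

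**Conclusion.** The concern holds in limited form. As written, no scheduled toxicity check or safety laboratory test follows a patient's final dose. Non-fatal grade 3+ events in that period, especially laboratory ones, can be under-recorded in the any-occurrence endpoint and the all-courses rate. The direction of bias is downward; its size cannot be derived from the documents. The 21% and 13% shares describe exposure to the gap under an assumed stopping pattern, and should not be read as bias in the per-patient rate.

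For deaths, the risk is that relation to eribulin is left unrecorded. The figures in step 4 show that the rule is sensitive to this, but m is assumed and nothing suggests a particular value.

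The point merits a small amendment. It does not touch the efficacy design, the sample size or any boundary.

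**What to change.** 1. In the Section 9.0 calendar, mark toxicity assessment, blood count and chemistry in the existing End of Study column, at an interval after the last dose that the plan states. Correlative blood is already drawn there.
2. In Section 13.0, say that findings at this visit enter the all-courses grade 3+ rate, and the course 1 rate for patients who receive only one course.
3. Require relation to eribulin to be recorded for every death, whenever it occurs, and state the rule by which a death enters the toxic-death count.
4. Set no end date on reporting of SAEs or suspected reactions. A cut-off would narrow duties that are now open-ended and would conflict with a count that has no time limit.

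Cost: one toxicity check and one routine blood test at an existing visit, and one item recorded per death. Reported toxicity rates may look slightly less favourable.

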10.1 ENDPOINT DEFINITIONS

10.1.1 PRIMARY EFFICACY ENDPOINT

Progression-free survival is defined as the time from first day of treatment to the first observation of disease progression or death due to any cause. If a patient has not progressed or died, progression-free survival is censored at the time of last follow-up.

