13.0 STATISTICAL CONSIDERATIONS

Study Design: This is a two-stage, single arm study to obtain preliminary evidence of efficacy of Eribulin in the treatment of recurrent cervical cancer. Current chemotherapy treatments for recurrent cervical cancer are associated with response rates and 6-month progression-free survival rates no higher than 10%. The objective of this study is to determine whether there is evidence that treatment with Eribulin will result in response and 6-month PFS rates that exceed 10%, suggesting promising activity and encouraging further study.

The primary efficacy endpoint will be 6-month progression-free survival (PFS₆). The secondary efficacy endpoint will be best overall response (BOR). A total of 30 patients who are fully evaluable for PFS₆ will be enrolled on this study. Patients who are not fully evaluable for PFS₆ will be replaced. Replaced patients will nonetheless be included in the final efficacy analysis. PFS₆ will be the endpoint for interim monitoring.

An interim analysis will occur when 15 patients have been evaluated for PFS₆, with final analysis once 30 patients have been evaluated for PFS₆. $\geq 1/15$ patients who achieve PFS₆ are required to continue study accrual to 30 patients. $\geq 6/30$ patients who achieve PFS₆ will be considered sufficient evidence of efficacy to warrant further study. The study will be terminated if fewer than 1/15 patients are progression-free at 6 months. The study may remain open pending the interim results on the first 15 patients, but will be suspended to enrollment if the 20th patient is enrolled before the interim results are available.

Sample size justification. This design has one-sided Type I error of <0.10 (0.072) for a true PFS₆ rate of 10%, and power of at least 0.80 for a true PFS₆ rate of 26%. Hence this study has sufficient power to detect moderate and clinical important improvements in PFS₆ rate due to Eribulin treatment when compared to past experience with chemotherapy treatment of recurrent cervical cancer.

Additional efficacy analyses. Product limits estimates of 6-month PFS will be computed using all patients enrolled on the study. 95% confidence intervals will be based on Greenwood standard errors. In addition, exact 95% binomial confidence intervals will be compute for the BOR rate.

Toxicity analyses. The rate of Grade 3+ hematology and non-hematologic toxicities will be computed for course 1 and for all courses combined.

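### No disease scan is set at 6 months, so for an undelayed patient the 6-month PFS count is in effect decided at the week-24 scan, and the stated error rates need not apply to it.

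*Combined protocol and SAP*

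**What the plan says.** - **Scans.** In the Section 9.0 calendar the row "Radiology, x-ray or Scans for disease measurement" is marked in the pre-treatment and every-2-cycles columns only. Section 7.0 sets a 21-day cycle. No scan is set at 6 months and no window is given.
- **Event date.** Section 10.1.1 defines PFS as the "time from first day of treatment to the first observation of disease progression or death due to any cause". It adds: "If a patient has not progressed or died, progression-free survival is censored at the time of last follow-up".
- **Decision.** Section 13.0 states: "The primary efficacy endpoint will be 6-month progression-free survival". Each patient is counted as achieving it or not. Accrual continues if at least 1 of 15 do, and at least 6 of 30 is a positive result.
- **Benchmark and error rates.** Section 13.0 describes current treatments as having "response rates and 6-month progression-free survival rates no higher than 10" per cent. It then says: "This design has one-sided Type I error of <0.10 (0.072) for a true" 6-month PFS rate of 10%, with "power of at least 0.80 for a true" rate of 26%.
- **Delays.** Under Section 8.2, if a Day 8 dose has to wait until Day 15, the site is to "administer eribulin at a reduced dose and initiate the next cycle no sooner than 2 weeks later". That cycle then lasts at least 28 days, and the cycle-based scan moves with it.

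**The concern.** The decision rule refers to one time point and the scans fall at others. For an undelayed patient the last look before 6 months is at week 24 and the next at week 30. Because the event is dated when it is first observed, a progression between week 24 and week 26 that shows only on imaging is recorded at week 30 and counted as a 6-month success. The count then measures status at about week 24, where the progression-free proportion is higher than at 6 months.

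In a 30-patient single-arm study whose verdict turns on 6 successes, one or two such patients can change the answer. The plan also does not say which scan decides 6-month status or how many weeks 6 months is, so two analysts could count the same patient differently.

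**Working it through.** **Inputs.** From Section 13.0: stage 1 needs at least 1 of 15, the final rule is at least 6 of 30, null 10%, alternative 26%. From Sections 7.0 and 9.0: 21-day cycles and a scan every 2 cycles. Assumptions that the documents do not supply: constant hazard, 6 months = 26 weeks, and (for the upper figures) progression found only on scans.

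**Step 1: the plan's own figures.** For a success probability p,

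P(go) = Σ over x = 1 to 15 of C(15,x) p^x (1−p)^(15−x) × P[Bin(15,p) ≥ 6−x].

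- p = 0.10 gives 0.0727, the stated 0.072 to within truncation.
- p = 0.26 gives 0.828, consistent with the stated power.

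The design arithmetic is sound if status is known at exactly 6 months.

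**Step 2: scan times.** 2 × 3 weeks = 6 weeks, so scans fall at weeks 6, 12, 18, 24 and 30.

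**Step 3: counted rate when week 24 decides.** With S(t) = 0.10^(t/26), S(24) = 0.119. P(go) at 0.119 is 0.140. At the alternative, 0.26^(24/26) = 0.288 and P(go) is 0.90.

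**Step 4: sensitivity.**
- If half of the progressions in the gap are caught in real time, by death or at a clinic visit, the counted rate is 0.10 + 0.5 × (0.119 − 0.10) = 0.110 and P(go) is 0.103.
- With Weibull shapes from 0.7 to 1.5 (and 6 months taken as 26.09 weeks), P(go) at week 24 runs from 0.12 to 0.19. The constant-hazard value on that scale is 0.143.

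**Step 5: delays.** One 1-week delay in the first 8 cycles moves the fourth scan to week 25: 0.10^(25/26) = 0.109 and P(go) 0.102. Two move it to week 26 and the gap closes. If each cycle has an independent chance of a 1-week delay and the total is capped at two, P(go) is 0.111, 0.092, 0.081 and 0.074 for chances of 10%, 20%, 30% and 50%.

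**Step 6: the opposite reading.** Suppose success required a clean scan after 6 months, at week 30. The null rate is 0.10^(30/26) = 0.070 and P(go) 0.016. At the alternative, 0.26^(30/26) = 0.211 and power is 0.63.

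| Scan that decides (undelayed) | Rate if truth is 10% | Type I error | Power if truth is 26% |
|---|---|---|---|
| Week 24 | 11.9% | 0.14 | 0.90 |
| Exactly 6 months | 10% | 0.073 | 0.83 |
| Week 30 | 7.0% | 0.016 | 0.63 |

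**The case against.** Five points can be made for the plan.

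1. *The endpoint is observed PFS, and the error rate is stated for that endpoint.* If the studies behind the 10% scanned at similar intervals, their figure carries the same effect and the bias largely cancels. This stands as a limit on the claim. The documents do not give that timing, so cancellation can be neither assumed nor ruled out.
2. *Progression is not found only on scans.* History and physical examination are marked every cycle, superficial lesions may be assessed clinically, and deaths count on the day. This stands, and it is why 0.14 is an upper figure for the undelayed schedule under a constant hazard.
3. *Six months could mean 24 weeks.* No section says so. If it did, the undelayed gap would vanish. A single 1-week delay would then put the fourth scan at week 25, after the mark, leaving week 18 or 19 as the last look before it.
4. *No deciding scan is named, so the bias has no fixed direction.* The first-observation definition points to the week-24 reading. A required later scan appears nowhere, and it would take power below the stated 0.80.
5. *Toxicity delays.* A reader might infer that repeated delays make matters much worse. Scans at weeks 7, 14, 21 and 28 would give a counted rate of 15.6% and a false-go chance of 0.32; unrestricted 1-week delays in 30% or 50% of cycles would give about 0.19 or 0.26. The documents do not support these as expected values. Section 8.2 makes a Day 8 delay for toxicity a trigger for permanent dose reduction, with two reduced levels and then discontinuation. A third such delay would therefore normally end treatment, apart from exceptions discussed with the principal investigator. Day 1 holds are not on that list, so larger drift is possible, but the documents give no frequency for it.

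**Conclusion.** The point holds in a limited form. Scans follow cycles, none is set at 6 months, and with PFS dated at first observation an undelayed patient's 6-month status is in effect fixed at week 24. The false-go chance is then about 0.14 rather than 0.072, or about 0.10 if half of the progressions in the gap are caught without a scan. This rests on a constant hazard, 6 months as 26 weeks, a true 6-month rate of 10%, and a benchmark free of the same scan-interval effect. One or two 1-week delays reduce the excess.

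Two stronger conclusions might be drawn and should not be. The first is that the schedule always favours eribulin: that depends on the first-observation reading, and a week-30 rule would push the other way. The second is that the stated type I error is shown to be wrong: it reproduces for status at exactly 6 months, and the real inflation depends on benchmark scan timing that is not given. What is established is that the schedule does not measure the time point on which the decision rests, and that neither available reading gives the stated operating characteristics under these assumptions.

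**What to change.** Schedule disease scans by calendar week from first dose, whatever the cycle delays: weeks 6, 12, 18 and 26, the last in a narrow window centred on 6 months, for example ± 1 week. Define 6-month PFS success as alive with no progression on or before that scan. State 6 months in weeks, and state how the studies behind the 10% timed their scans, if known.

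The window should be centred. In the same model a scan at week 25 gives type I error 0.10 and power 0.87, and one at week 27 gives 0.05 and 0.78, so scans spread evenly around week 26 stay close to the design values. A window of 0 to +2 weeks, with progression on that scan counted as failure, would overcorrect: at week 28 the figures are 0.035 and 0.74.

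The cost is a calendar and endpoint-wording amendment. No scan is added up to 6 months, because the fourth moves from week 24 to week 26. The downsides are one 8-week gap between scans, scans that do not always coincide with a cycle visit, and a slightly lower observed 6-month PFS.
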